- 1) The proposed regimens can be delivered in only **two weeks or less**, increasing compliance and tolerance for HNSCC patients and decreasing omission, delays or breaks in post-operative radiation, which represent major causes of disease relapse. Since substantial radiation toxicities do not typically begin until the third week of treatment, delivering post-operative radiation in only two weeks or less should lead to high compliance rates without treatment breaks. Further, HNSCC patients' ability to receive consistent post-operative radiation can be limited by travel distance and transportation challenges often related to social determinants of health including socioeconomic status, rural setting, and race. Patients of black race, Hispanic ethnicity, or with Medicaid insurance are significantly less likely to travel long distances for treatment. As such, these groups are less likely to receive care at academic and high-volume centers, more likely to have treatment breaks, and have worse survival outcomes. By condensing therapy from six weeks to two or less, this regimen will lessen the financial and psychosocial burden of radiotherapy and may reduce disparities in treatment and outcomes by facilitating greater access to care. Further, we have shown that in interviews of a subset of our patient population who refused adjuvant radiotherapy, 75% would have undergone radiation if it were completed in two weeks or less, leading us to select regimens that could be delivered in this time frame (10, 8 and 5 fractions).
- 2) These three regimens target a biologically effective dose (BED) will of ~100 Gy for an  $\alpha/\beta=3$  for all dose levels. An important risk of hypofractionated regimens is late toxicity to normal tissues. The design of these three proposed dose levels, however, maintains an acceptable BED to late-responding tissues that is consistent with the BED3 (100 Gy) of conventional postoperative radiation of 60 Gy in 30 fractions:

Total dose(Gy)/number of fractions	Dose per fraction (Gy)	a/b 10 (Gy)	a/b 3 (Gy)
42/10	4.2	59.64	100.8
39/8	4.875	58.01	102.3
32.5/5	6.5	53.6	102.9

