### 1.3 Study Innovation

Several aspects of the HART-HN framework (**Figure 2**) for delivering post-operative radiation to patients with mucosal HNSCCs are innovative.

- a. Compressed Time Frame:** Unlike conventional post-operative radiation, which is delivered to a total dose of 60 Gy in 30 fractions over six weeks, HART-HN would be delivered to a total cumulative dose of 32.5-42 Gy in five to ten fractions over one to two weeks. Though the cumulative radiation dose for HART-HN is lower than for conventional post-operative radiation, we predict HART-HN to be at least as efficacious as conventional post-operative radiation for HNSCCs based on both empiric principles and analogous data from other malignancies. Accelerated repopulation of tumor cells after surgery and during radiotherapy is a principle mechanism of treatment failure in HNSCCs. From tumor line models, the estimated kickoff time for such repopulation is estimated at 21-35 days after initiation of therapy. As post-operative radiation is usually initiated as soon as three to four weeks after surgery, patients receiving HART-HN will complete surgery and radiation therapy within 30-45 days, before tumors begin to rapidly repopulate, thus reducing the risk of failure. Given the short treatment time-course we also anticipate that breaks in radiotherapy will be unlikely. Additionally, radiation regimens similar to HART-HN have long been used in post-operative treatment of resected melanomas with excellent LRC upwards of 90%.

**Figure 2.** Comparison of conventional post-operative radiation (PORT) and HART-HN. HART-HN reduces the overall treatment time compared to conventional therapy allowing patients to initiate and complete adjuvant radiation prior to developing acute effects of therapy and reducing overall treatment package time. Patients receiving HART-HN may have a shorter total duration of acute effects of therapy (yellow) and therefore tolerate it better than conventional therapy.

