Until now, the safety and efficacy of the radiotherapy dosing regimen proposed for HART-HN has not been evaluated for mucosal HNSCCs. This is because delivering such high doses per fraction was previously unfeasible due to limited image guidance capabilities and an inability to deliver precisely targeted (conformal) radiotherapy, resulting in undue toxicities to the sensitive mucosal structures of the head and neck. With the development of IMRT, it should be feasible to safely deliver this regimen post-operatively for mucosal HNSCCs while protecting critical structures including the spinal cord and brainstem.

- b. Improved QOL:** HART-HN is innovative in its promise to reduce the duration of acute toxicity in patients receiving treatment for HNSCCs. As depicted in Figure 2, acute radiation toxicities usually begin about 2 weeks after the initiation of radiation. These toxicities continue to escalate in intensity, reaching a maximum about 1 week after completion of treatment and resolving about one month after treatment. This delayed response occurs since acute toxicity is reflective of radiation effects on rapidly dividing tissues such as the epithelium of the skin and oral mucosa. Radiation preferentially kills rapidly dividing cells and toxicity manifests when these epithelial regions are not sufficiently repopulating, leaving a denuded epithelium. As new stem cells repopulate the area (when radiation completes), toxicity resolves. Prior to the epithelium being denuded, there is no acute toxicity.

With HART-HN, we anticipate a similar onset of symptoms about one week after treatment, as the epithelium likely will not denude until completion of treatment. Thus, patients will complete their adjuvant

treatment with HART-HN prior to developing significant acute effects, reducing the risk of treatment breaks or early discontinuation of therapy. Assuming that the acute effects of HART-HN persist for a similar duration after completion of therapy as they do for conventional post-operative radiation due to similar speed of stem cell repopulation, patients will recover from acute effects of HART-HN before patients would have even completed conventional post-operative radiation. This should reduce patient pain and the duration of opioid therapy, ultimately improving QOL.

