### **2.3 Primary Endpoint**

The primary endpoint of the study is to find the maximum tolerated dose density for radiation regimens with a BED3 = 100 Gy, that may be safely delivered for the HART-HN regimen in patients with resected HNSCC with intermediate pathologic risk features.

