Patients will undergo standard consultation to receive adjuvant head and neck radiotherapy for HNSCC and will be determined to be eligible for the clinical trial. If eligible, patients will receive informed consent about the risks and benefits of the trial and if they accept, will sign confirming their enrollment. Patients will then undergo standard radiotherapy simulation including CT simulation with and without IV contrast and/or MRI simulation with and without Gadolinium contrast. Patients will complete baseline FACT-HN and MDADI surveys. Patients will also be followed with a speech and language pathologist (SLP) and undergo videofluoroscopic swallow studies (VFSS) prior to treatment, 3 months after treatment and 6 months after treatment, as is standard of care in the treatment of HNSCCs and will be graded by the Dynamic Imaging Grade of Swallowing Toxicity (DIGEST) scale.

A radiation treatment plan will be developed as per the details in Section 5.1 with two target volumes: the PTV\_High (defined as the operative bed plus a 3 mm margin) will receive the experimental dose over the experimental number of fractions (BED3 of ~100, the BED3 of 60 Gy in 30 fractions) and the PTV\_Low (elective lymph node regions plus 3 mm setup margin) will receive a subclinical dose over the experimental number of fractions (BED3 of ~86.4, the BED3 of 54 Gy in 30 fractions).

Patients will then undergo daily image-guided radiotherapy on a Monday-Friday basis for the total number of experimental fractions. During treatment, all patients will be evaluated for acute toxicities at least once every five fractions with a physician visit. Additionally, patients will complete repeat FACT-HN and MDADI surveys on the day of treatment review.

After completion of the HART-HN, patients will be seen in follow-up at the following time points after completion of radiotherapy: bi-weekly for the first 6 weeks, at 3 months, 6 months, 9 months and 12 months. Patients will complete repeat FACT-HN and MDADI surveys to assess for quality of life outcomes at each follow-up. Repeat imaging including a PET/CT or Chest CT (with or without contrast) and a diagnostic CT (with or without contrast) or MRI of the neck will be ordered at the 3-month (+/- 2 weeks) follow-up timepoint. A head and neck CT or MRI may be ordered at any time, if clinically indicated.

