#### 5.1.4.1 Dose Fractionation

Once daily radiation will be delivered as per the enrolled dose level of the patient:

	Target	Dose Level 1	Dose Level 2	Dose Level 3
D PTV_High	PTV_High	42 Gy in 10 fx	39 Gy in 8 fx	32.5 Gy in 5 fx
D PTV_Low	PTV_Low	38 Gy in 10 fx	34 Gy in 8 fx	29 Gy in 5 fx

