## 7.2 Objectives and Analysis Plans

### 7.2.1 Primary Objective and Analysis Plan

The primary objective of the study is to determine the safe reduction of the number of fractions (10, 8, or 5), that may be delivered safely in resected HNSCC patients with intermediate pathologic risk features.

The minimum number of safe fractions will be determined as the radiation dose at which there is no more than a 33% rate of dose-limiting toxicity (DLT) up to 12 months after completion of radiation treatment (to allow for the development of late toxicities from radiation treatment) using the TITE-CRM design.

A DLT will be defined for the purposes of this protocol as an inability to complete radiation treatment within 30 days of the start of radiotherapy not deemed to be related to disease progression or unrelated death, unacceptable toxicity within one year of treatment (Grade 4+ toxicity) probably or definitely related to radiation treatment as deemed by the treating physician, or a death within one year of treatment deemed probably or definitely related to treatment. Expected Grade 3 acute toxicities typical of head and neck radiation that resolve within 90 days of treatment, including acute dermatitis, acute mucositis, feeding tube placement, electrolyte abnormalities, pain requiring narcotic medication and dehydration requiring IV hydration will **NOT** be considered DLTs. Grade 4+ late toxicities that may be considered a DLT of radiation include but are not limited to:

- Chondronecrosis of the laryngeal cartilages
- Laryngeal edema requiring tracheostomy
- Carotid blowout syndrome or other life-threatening vascular bleed
- Aspiration pneumonia requiring ICU admission not related to tumor progression
- Chronic non-healing wound or soft tissue necrosis requiring flap reconstruction
- Brainstem necrosis
- Radiation myelopathy

Death deemed unrelated to radiation (such as death due to malignancy or other comorbidity) will not be considered a DLT.

All patients who initiate radiation therapy will be evaluable for the primary endpoint as long as they initiate radiation therapy.

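### The DLT's non-completion limit is 30 days from the start of radiotherapy at all three levels, so it tolerates the longest break in the shortest, most condensed course

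*Combined protocol and SAP*

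**What the plan says.** Section 7.2.1 gives the DLT three limbs. The first is an "inability to complete radiation treatment within 30 days of the start of radiotherapy", unless this is put down to progression or to a death unrelated to treatment. The others are Grade 4 or higher toxicity, and death, within a year and judged probably or definitely related to treatment. The section also carves out "Expected Grade 3 acute toxicities typical of head and neck radiation that resolve within 90 days of treatment", which are not DLTs.

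Delivery is the same at every level. Section 3.1 plans "daily image-guided radiotherapy on a Monday-Friday basis for the total number of experimental fractions", and section 5.1.4.1 adds "Once daily radiation will be delivered as per the enrolled dose level of the patient". The levels have 10, 8 and 5 fractions. The protocol gives no level-specific completion limit and no maximum break, and it does not say whether the 30 days count the first fraction as day 1 or are elapsed days.

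Section 2.3 defines the primary endpoint as finding "the maximum tolerated dose density for radiation regimens" of fixed late-tissue effect.

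**The concern.** A 30-day clock allows more delay the shorter the planned course. The limb is therefore strictest for the 10-fraction regimen and loosest for the 5-fraction regimen that the trial hopes to reach. Dose density depends on overall time, so a one-week course stretched over four weeks has not shown that the one-week schedule is tolerated. Under this limb it would still count as completed.

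The other limbs do not fill the gap. Expected Grade 3 acute toxicity that resolves within 90 days is excluded. For toxicity below Grade 4, this limb is therefore the only one that can register a long break in a course that is later finished. With 18 patients, and a TITE-CRM that uses all accumulated outcomes for each new assignment, the limb should mean the same thing at each level.

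**Working it through.** **Inputs.** Fractions n = 10, 8, 5 (sections 5.1.4.1 and 7.1); one fraction per weekday (sections 3.1 and 5.1.4.1); limit of 30 days from the start (section 7.2.1). I assume no public holidays or machine closures. With m missed weekdays the last fraction falls on weekday number n + m from the start, so the position of the break does not matter.

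**Step 1: planned last fraction (first fraction = day 1).**

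| Start weekday | Level 1 | Level 2 | Level 3 |
|---|---|---|---|
| Mon | 12 | 10 | 5 |
| Tue, Wed | 14 | 10 | 7 |
| Thu, Fri | 14 | 12 | 7 |

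This reproduces the one to two weeks stated in section 1.3. Calendar slack to day 30 is 16-18, 18-20 and 23-25 days at Levels 1, 2 and 3, and one day more under an elapsed-day count.

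**Step 2: weekdays available, W.**
- Count A, last fraction by day 30: 30 = 4 × 7 + 2, so 20 weekdays plus those in the two remaining days. W = 22 for Monday to Thursday starts and 21 for Friday.
- Count B, 30 elapsed days, last fraction by day 31: W = 23 for Monday to Wednesday starts, 22 for Thursday and 21 for Friday.

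**Step 3: largest break that is not a DLT under this limb, W − n.**

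| Level | Count A | Count B |
|---|---|---|
| 1 (n = 10) | 11-12 | 11-13 |
| 2 (n = 8) | 13-14 | 13-15 |
| 3 (n = 5) | 16-17 | 16-18 |

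For any one start weekday and day count, Level 3 tolerates exactly 10 − 5 = 5 more missed weekdays than Level 1, and Level 2 tolerates 10 − 8 = 2 more.

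**Step 4: breaks classified differently whatever the start day or count.** With m = 14, 15 or 16, Level 1 finishes on weekday 24, 25 or 26. All exceed the largest W of 23, so the limit is always missed. Level 3 finishes on weekday 19, 20 or 21. None exceeds the smallest W of 21, so the limit is always met. In calendar terms, 15 missed weekdays move the end by 21 days: to day 33-35 at Level 1, day 31 or 33 at Level 2, and day 26-28 at Level 3. At Level 2 that misses the limit for all five start weekdays under count A, but only for Thursday and Friday starts under count B.

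**Step 5: relative to planned length.** Level 1 may stretch to 30/14 = 2.1 up to 30/12 = 2.5 times its plan. Level 3 may stretch to 30/7 = 4.3 up to 30/5 = 6.0 times.

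**Step 6: check of a replacement.** The day 14 days after the planned last fraction is the same weekday two weeks later. The maximum is then exactly 10 missed weekdays at every level, for every start weekday, however day 1 is counted. An allowance of 16 days (Level 1's smallest calendar slack) does not do this. For Monday to Friday starts it gives 10, 12, 12, 12, 11 at Levels 1 and 3 but 12, 11, 10, 12, 12 at Level 2, so breaks of 11-12 weekdays stay level-dependent.

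**The case against.** **Few patients will fall in the gap.** The levels differ only for breaks of about 12 to 17 missed weekdays (count A) in a course that is later finished, without related Grade 4 or higher toxicity. The protocol says "we also anticipate that breaks in radiotherapy will be unlikely", that "substantial radiation toxicities do not typically begin until the third week of treatment", and, for this regimen, "we anticipate a similar onset of symptoms about one week after treatment". A 5-fraction course is planned to end by day 5-7, so a long toxicity-driven break inside it should be rare. This stands, and it limits the weight of the point.

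**The serious cases are caught anyway.** Permanent non-completion (outside the two exceptions), related Grade 4 or higher toxicity and related death are DLTs at every level. A reader might infer that severe toxicity at Level 3 could escape the DLT altogether. The text does not support that.

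**A fixed clock can be defended.** Section 1.3 argues in elapsed time: repopulation starting at 21-35 days, and surgery plus radiation finished within 30-45 days. A single calendar limit is compatible with this, and extra slack for a shorter course is not in itself an error. But the protocol does not give this as its reason, and the limit does not enforce that aim. If radiation starts 21-28 days after surgery, finishing at the limit means 21 + 29 = 50 to 28 + 30 = 58 days.

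**The limb speaks of inability, not of a day count.** A reader might infer that any three-week break, whatever its cause, is automatically a DLT at Level 1. The wording leaves room for judgement about voluntary or logistical breaks. The point therefore covers breaks that make the patient unable to finish in time.

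**Conclusion.** The inconsistency is real. This limb tolerates five more missed weekdays at Level 3 than at Level 1, and breaks of 14-16 missed weekdays that prevent timely completion are DLTs at Level 1 and not at Level 3, under either day count. The direction is lenient towards the most condensed regimen. The result rests on once-daily weekday delivery without holidays.

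A reader might infer that the trial is biased towards selecting five fractions. The documents do not show that. They give no rate of breaks, so neither the number of patients affected nor the shift in level selection can be calculated, and the protocol's own expectations suggest that both are small. This is an optional, inexpensive correction to the primary endpoint's definition, and it does not undermine the design.

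**What to change.** In section 7.2.1, replace the 30-day limit with one that is identical at every level, for example: *within 14 calendar days after the planned last fraction of the assigned dose level (equivalently, a DLT if more than 10 treatment weekdays are missed)*. Keep the two existing exceptions and the Grade 3 exclusion unchanged. To stay closer to Level 1's present tolerance, state the limit as more than 11 missed treatment weekdays instead. Report actual overall treatment time by level beside the DLT result. Section 4.1 already defines on-treatment status by the first and last treatment days.

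The cost is one sentence in an amendment, with no change to sample size or model. There are three downsides:
- The 14-day version tightens Level 1 by 1-2 missed weekdays (12 or 11 down to 10), and by up to 3 under the elapsed count (13 down to 10).
- A few long breaks at Levels 2-3 that now go uncounted become DLTs, including some not caused by toxicity. With 18 patients, even one could influence an assignment.
- The allowance is equal in absolute terms only. Level 3 could still run to (7 + 14)/7 = 3.0 up to (5 + 14)/5 = 3.8 times its planned length, against (14 + 14)/14 = 2.0 up to (12 + 14)/12 = 2.2 at Level 1.

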To assess efficacy of the HART-HN regimen assessment of locoregional control and overall survival will be made by the treating radiation oncologist or surgeon at each follow-up, by clinical examination of the head and neck as per the standard of care. Standard post-treatment imaging including a neck CT (with or without contrast) or MRI and a chest CT (with or without contrast) or PET/CT (with or without contrast) will be obtained at 3 months post-treatment (+/- 2 weeks), as per standard of care. Additional surveillance imaging in the follow-up setting has not shown any benefit in 3-year disease-free survival as compared to ongoing clinical surveillance. Therefore, patients will be clinically followed for disease control until locoregional progression, completion of the 12-month follow-up period, patient refusal, or death.

In order to understand the acute and long-term toxicities of the HART-HN regimen patients will be followed clinically by the treating radiation oncologist, undergo routine FACT-HN and MDADI surveys, and undergo scheduled SLP visits including VFSS and DIGEST grading as detailed in the prior section. For the purposes of this study, acute toxicity will be deemed any toxicity that occurs within 90 days of completion of radiation therapy, and late toxicity will be deemed any toxicity that occurs more than 90 days after completion of radiation therapy. During each weekly treatment review and each post-treatment follow-up, the treating physician will record a pain score (scale 1-10) and use the Common Terminology Criteria for Adverse Events Version 5.0 (CTCAE) to record toxicity scores for dysphagia, oral mucositis, dehydration and weight loss. The treating physician will also record tracheostomy tube dependence and feeding tube dependence at each visit.

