### 6.1.4 Attribution of an Adverse Event

All AEs and SAEs whether volunteered by the subject, discovered by study personnel during questioning, or detected through physical examination, laboratory test, or other means will be reported appropriately. Each reported AE or SAE will be described by its duration (i.e., start and end dates), regulatory seriousness criteria if applicable, suspected relationship to study intervention (see following guidance), and actions taken.

An assessment of the relationship between the adverse event and the medical intervention, using the following categories:

**Definitely Related:** *The AE is clearly related to the intervention.* There is clear evidence to suggest a causal relationship, and other possible contributing factors can be ruled out.

**Probably Related:** *The AE is likely related to the intervention.* There is evidence to suggest a causal relationship, and the influence of other factors is unlikely.

**Possibly Related:** *The AE may be related to the intervention.* There is some evidence to suggest a causal relationship (e.g., the event occurred within a reasonable time after administration of the trial intervention). However, the influence of other factors may have contributed to the event (e.g., the subject's clinical condition, other concomitant events).

**Unlikely:** *The AE is doubtfully related to the intervention.* A clinical event, including an abnormal laboratory test result, whose temporal relationship to drug administration makes a causal relationship improbable (e.g., the event did not occur within a reasonable time after administration of the trial intervention) and in which other drugs or chemicals or underlying disease provides plausible explanations (e.g., the subject's clinical condition, other concomitant treatments).

**Unrelated:** *The AE is clearly NOT related to the intervention.* The AE is completely independent of study intervention, and/or evidence exists that the event is definitely related to another etiology.

To ensure consistency of AE and SAE causality assessments, investigators should apply the following general guideline:

Yes: Related (definitely, probably, possibly, unlikely)

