**Table 2**

Attribution	SAE				AE		
	Grade 1, 2 & 3		Grade 4 and 5		Grade 3	Grade 4	
	Expected	Unexpected	Expected	Unexpected	Unexpected	Expected	Unexpected
Unrelated Unlikely	IRB  and DSMC- Routine Review 	IRB  and DSMC- Routine Review 	IRB  - Routine Review 	IRB  - Routine Review 	DSMC  - Routine Review	DSMC  - Within 5 calendar days	DSMC  - Within 5 calendar days
Possible Probable Definite		IRB  and DSMC  - Within 5 calendar days	DSMC  - Within 5 calendar days	IRB  and DSMC  - Within 5 calendar days			

Guidance on Adverse Event Reporting to the IRB is available online at [MCW IRB Policies and Procedures](#).

For routine reporting, the events will be reported to IRB as part of the annual continuing progress report, and the DSMC will review events entered in OnCore® at the time of scheduled monitoring.

For expedited DSMC reporting, study coordinator/research nurse must notify the DSMC via email. For AEs, include the subject ID, date of event, grade, relatedness, expectedness, and a short narrative. For SAEs, DSMC will review the SAE report entered into OnCore®.

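### Section 7.2.1 leaves Grade 3 toxicity persisting beyond 90 days open to two DLT readings and, as worded, can score non-completion from an unrelated illness as a DLT

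*Combined protocol and SAP*

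**What the plan says.** Section 7.2.1 gives three routes to a DLT.

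- **Non-completion:** "inability to complete radiation treatment within 30 days of the start of radiotherapy not deemed to be related to disease progression or unrelated death".
- **Toxicity:** "unacceptable toxicity within one year of treatment (Grade 4+ toxicity) probably or definitely related to radiation treatment as deemed by the treating physician".
- **Death** within a year, again only if probably or definitely related to treatment.

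The next sentence removes certain events from the count: "Expected Grade 3 acute toxicities typical of head and neck radiation that resolve within 90 days of treatment, including acute dermatitis, acute mucositis", with feeding tube placement, electrolyte disturbance, pain needing narcotics and dehydration needing IV fluids also listed. A list of late events follows, introduced by "Grade 4+ late toxicities that may be considered a DLT of radiation include but are not limited to". Section 3.1 sets the boundary between acute and late: "late toxicity will be deemed any toxicity that occurs more than 90 days after completion of radiation therapy".

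The minimum safe number of fractions is the regimen with "no more than a 33% rate of dose-limiting toxicity (DLT) up to 12 months after completion of radiation treatment". Section 7.3 cites an institutional one-year rate of 9.5%, which is a Grade 4+ rate.

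Section 4.7 lists reasons for ending treatment that include intercurrent illness, the subject's decision to withdraw, and noncompliance. Such subjects are not replaced, and Section 7.2.1 keeps everyone who starts radiation evaluable for the primary endpoint.

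**The concern.** Two assessors applying Section 7.2.1 in good faith could score the same patient differently. A patient with a related Grade 3 event, such as feeding tube dependence, that is still present four months after radiation is not a DLT under the toxicity criterion, because the grade is too low. The patient also falls outside the exemption, because the event did not resolve in 90 days. The case can be expected to arise: Section 3.1 has the physician record feeding tube dependence at every visit.

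The non-completion criterion raises a different problem. It can put an event with no connection to radiation toxicity into the DLT count, while the other two criteria require probable or definite relatedness.

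DLT status feeds each dose assignment and the pause before escalation (Section 7.1) and the MTD (Section 7.2.1). It also feeds the stopping rule in Section 7.4, if the 12-month quantity compared there with 33% is read as the DLT rate; the noun is missing from that sentence. With 18 patients over three levels, individual classifications matter.

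**Working it through.** **1. The Grade 3 sentence under each reading**

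| Event (related to radiation) | Grade 4+ only | 90-day condition has effect |
|---|---|---|
| Expected acute Grade 3, resolved within 90 days | Not a DLT | Not a DLT |
| Grade 3 still present after 90 days | Not a DLT | Can be a DLT |
| Grade 4+, probably or definitely related, within one year | DLT | DLT |

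Only the middle row differs. The first reading makes the conditions (expected, acute, resolved) redundant. The second needs a positive rule for Grade 3 that is nowhere written.

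**2. The non-completion criterion**

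Take a patient who starts radiation and cannot finish within 30 days because of an unrelated intercurrent illness. The cause is neither disease progression nor death, so neither exemption applies. The patient is evaluable and not replaced, so the result is a DLT. Voluntary withdrawal is unclear: the text does not say whether it is an inability to complete.

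**3. The plan's own figures**

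- Accrual reproduces: 25% of 6 per month = 1.5 per month, and 18 / 1.5 = 12 months.
- The MTD-selection table in Section 7.3 did not reproduce. For assumed rates of 5/15/30% the plan reports 15.9%, 28.2%, 55.9% and 0.0% (Levels 1, 2, 3, stop). Across 14 skeletons, two selection rules and several prior variances, the best variant's largest cell deviation over the four scenarios was 21 points. The skeleton and prior variance are not stated, so this does not show the table is wrong. The results below are therefore sensitivity checks, not corrections of it.

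**4. Can one reclassified patient change the MTD?**

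Assumptions: empiric power model (rate = skeleton^exp(b)), normal prior on b with variance 1.34, target 33%; 3, 6 and 9 patients at Levels 1, 2 and 3, all followed for 12 months; no DLT at Level 1 and one at Level 2. With skeleton 0.178/0.33/0.49, choosing the level closest to 33%:

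| DLTs at Level 3 | Estimate, Level 2 | Estimate, Level 3 | Distance from 0.33 (Levels 2; 3) | Selected |
|---|---|---|---|---|
| 1 | 0.087 | 0.208 | 0.243; 0.122 | Level 3 |
| 4 | 0.223 | 0.381 | 0.107; 0.051 | Level 3 |
| 5 | 0.273 | 0.433 | 0.057; 0.103 | Level 2 |

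The switch between 4 and 5 DLTs also occurs with skeletons 0.233/0.33/0.431, 0.145/0.33/0.529 and 0.095/0.20/0.33. If the rule is instead the highest level estimated at or below 33%, Level 2 is first selected at 3 or 4 DLTs, depending on the skeleton. At 0 or 1 DLT, one more changes nothing under either rule.

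**5. Effect on the DLT rate**

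The documents give no rate q of related Grade 3 toxicity unresolved at 90 days. Assume q = 15% (range 5-25%), independent of Grade 4+ events. The combined rate is 1 - (1 - p)(1 - q), where p is the Grade 4+ rate.

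- p = 10%: 1 - 0.90 x 0.85 = 23.5% (range 14.5% to 32.5%). It stays below 33% throughout.
- p = 25%: 1 - 0.75 x 0.85 = 36.25% (range 28.75% to 43.75%). It exceeds 33% once q is above 1 - 0.67/0.75 = 10.7%.

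**6. Effect on selection over repeated trials**

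These simulations used N = 18, the plan's accrual, 75.4% survival, the three-patient rule and the pause, with four skeletons and both selection rules. Counting persistent Grade 3 events was taken to add a fixed amount to every level's DLT rate.

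- Adding 5 points lowered selection of Level 3 by about 15-22 points.
- Adding 10 points lowered it by about 26-39 points.
- Example (skeleton 0.178/0.33/0.49, closest rule), for added 0, 5 and 10 points: 78%, 62%, 42% when Grade 4+ rates are 5/15/30%; 75%, 55%, 39% when they are 10/15/25%.

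With 250-400 runs per setting, a percentage near 50% has a standard error of 2.5 to 3.2 points. Part of the fall is the design working properly, because 30 + 5 = 35% exceeds the limit. In the second scenario, however, 25 + 5 = 30% is still within it.

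**The case against.** The best defence is that the intended meaning is already visible. The only affirmative toxicity rule is Grade 4+, the late-event list is headed Grade 4+, and the benchmark is a Grade 4+ rate. The Grade 3 sentence can be read as a redundant reassurance. This largely stands: it rules out calling the definition a flat self-contradiction, because the second reading arises only by implication. It does not remove the implication.

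On non-completion, the criterion does contain a causal exclusion, so it would be wrong to say it has no relatedness test. A one- to two-week course with a 30-day window should also make such cases uncommon. Both points stand, but the exclusions are still narrower than the treatment-stopping reasons in Section 4.7.

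A reader might also infer that relatedness cut-offs elsewhere change the DLT count. Table 2 groups "Possible Probable Definite" together, and Section 6.1.4 has "Yes: Related (definitely, probably, possibly, unlikely" as its related category. The documents do not support that inference. Section 6.2.3 presents Table 2 as identifying events for reporting, and Section 7.2.1 carries its own threshold, so Table 2 changes the DLT count by zero. A wider net for reporting than for DLTs is not an inconsistency, and nothing here shows that DLTs ought to include possibly related events. Sections 6.1.4 and Table 2 do disagree on which side *unlikely* falls, but that is a separate reporting matter.

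Finally, the simulated scenarios are generic one-year toxicity rates from 5% to 60%, tied to no grade. They cannot be said to fit only the Grade 4+ reading.

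**Conclusion.** The concern holds in two parts. The DLT status of Grade 3 toxicity persisting beyond 90 days is open to two readings, with the Grade 4+ reading the better supported. The non-completion criterion, read literally, counts an unrelated intercurrent illness as a DLT and leaves voluntary withdrawal undefined.

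The consequence is conditional. Near the decision boundary one reclassified patient can change the selected level; at low counts it does not, so the stronger inference that any one or two reclassified events move the MTD is not supported. The rate and selection effects rest on assumed values of q, on independence in step 5 (positive correlation would shrink the combined rates), and on assumed skeletons and priors. They show that the reading can matter, not how much it will. Because this is the trial's only toxicity endpoint and the repair is mainly wording, it should be settled before the next dose assignment.

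**What to change.** In Section 7.2.1:

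- State explicitly whether Grade 3 events outside the exemption are DLTs. If Grade 4+ only is intended, delete the 90-day qualifier. The sponsor chooses the clinical threshold.
- Align the non-completion criterion with the attribution requirement of the other two, so that non-completion for reasons unrelated to radiation is not scored as toxicity. Say how voluntary withdrawal is classified, and check the wording against the stopping reasons in Section 4.7.
- Confirm that the 9.5% benchmark and the Section 7.3 simulations use the definition kept. If Grade 3 events are to count, the benchmark needs a matching figure and the assumed rates need review.
- Apply the settled definition to every patient already treated before the model is next run.

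Separately, reconcile Section 6.1.4 with Table 2 on *unlikely*; this does not touch the DLT count.

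The cost is a protocol amendment and matching case report form wording. Toxicity grades, attribution, event dates and feeding tube status are already collected. Further simulation is needed only if the sponsor adopts the broader Grade 3 definition or finds that the existing runs assumed a different one.
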